### 5. Describe the main challenges implementing PBE.

We believe this DAP underlines many of the challenges of *analysing* PBE data. One particular challenge, affecting all the above analyses, is that of non-participation. The relatively small issue of missed items has been noted above but other missing data is likely to be far more important. For all the analyses described above we will describe initial refusals and withdrawals and will also report data loss by exclusions and administrative errors and explore how these may have affected data.

Particular attention will be paid to cohort/time changes in missingness, and to differences between centres. It is recognised that recruitment since the coronavirus (CV-19) pandemic will have been affected and this will be studied specifically against the timing of the public health measures imposed and how ITA reacted made operational changes. These analyses are expected to be conducted in all the three tranches.

Given that none of the missingness is likely to be truly "Missing at Random" (MAR) let alone "Missing Completely at Random" (MCAR) we believe that the sophisticated imputation methods, such as Multiple Imputation by Chained Equations (MICE), which are powerful and unbiased for MCAR, and strong for some MAR models, may have limited or no advantages over crude substitutions (means across all participants for the missing data, or means for that participant) or simple deletions (listwise/casewise) all of which can introduce strong biases into analyses. We will use methods, in the light of the observed patterns of missingness, and report their impacts on analyses as robustness checks rather than as solutions for missingness.

In addition to these data analytic challenges, many of which are far more severe than for analysis of trial data, and are consequently less explored, there are simple challenges of implementing PBE data collection without substantial research funding. We will describe qualitatively, the challenges and how we sought to manage and mitigate them, where possible. Where, as with missingness, quantitative data throw light on success or failure of mitigation, these data will be reported.

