#### 2. Planned and emergent analyses

Many analyses will be conducted to address the study objectives and these are summarised below. As noted, the complexity of the data will certainly lead to the performance of emergent analyses. These will always be defined as such, against this DAP, in any presentations, reports or papers. All publications will be made with the (Altman & Moher, 2013) transparency statement which will apply to the distinction between *a priori* and emergent analyses as much as to all important issues to be acknowledged transparently.

The analysis timing has been designed in three tranches.

- The first tranche will focus on the baseline data for participants recruited during the first three years. The most important focus will be to establish the baseline distributions of variables that will be used later to measure change, the psychometric properties of

those measures, the differences between clinical centers, and any strong associations between baseline variables likely to raise issues about confounding in the subsequent analyses of change.

- The second tranche will contain all data collected by the end of October 2020: the endof the intensive data collection phase. When analysing these data, the focus will be on change: changes in sociodemographic variables (assessed annually) and clinical interventions but primarily changes in the key clinical outcome variables of the questionaire scores and BMI.
- The third tranche will add the follow-up information for all the participants recruited to October 2020 as and followed-up, where in continued clinical contact with the services, to November 2025. The main analyses for this tranche will largely follow the explorations of change, its diversity and its predictors as from the second tranche.

Here we present the a priori analyses planned for each objective and broken down by tranche.

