# 3. Primary objective: Effectiveness of ITAMITED as it is applied routinely in its natural context.

We will analyse effectiveness with three complementary analyses performed for data/analysis tranches 2 and 3.

(a) Baseline/termination change. This is has been the traditional focus of many existing explorations of effectiveness of treatment. We will report both mean change and also effect sizes reporting Cohen's d2 and dz (Cohen, 1988) (the ratio of mean change to baseline SD and the ratio of mean change to SD of change respectively) and report these with bootstrap CIs. As well as reporting the global aggregate mean shifts with bootstrap 95% CI for each score. We will report the regression of termination scores on baseline scores and the distributions of change scores.

We will explore the impact of baseline variables: gender, age, diagnosis, demographic

variables, medication use and service on change. These predictor effects will be explored entering them as predictors of termination scores/values in ANOVA models with attention paid to the almost certain violation of assumptions of the ANOVA and exploration of mitigation of those violations. As gender and age are such crucial variables in Eating Disorders (Eds) the effects of entering these as predictors (or analysing separately be gender) on effects of other variables will be reported.

To address individual change we will report the Jacobson plot of termination against baseline scores for all scores and report the RCSC breakdown of change on each measure where it is possible to define the CSC and RCI.

(b) Multilevel models (MLM) of rates of change. MLM allows analysis of change slopes across diverse durations of therapy/ascertainment and the method handles the nonindependence of observations arising from the repeated measures within participant appropriately. These analyses can give a much more nuanced picture of change than baseline/termination analyses while allowing exploration of the effects of the same predictors and covariates analysed in (a). As for (a), durations of therapy are not directly reflected in the analyses though in contrast to (a), all data across all durations of data collection are used rather than just the first and last values.

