(c) Survival analysis (e.g. Allgulander & Fisher, 1986; Singer & Willett, 2003; Willett & Singer, 1993)for time to terminations by category of termination. These analyses focus on the time spans between entry into treatment and termination which are not so focal in (a) and (b). The particular strength of survival analysis for a naturalistic cohort follow-up study is that it address the inevitable right censoring of follow-up. That is that at termination of intensive data collection some participants will be still in treatment so their "outcome" is only know to this point and how long each has been in treatment to that point will be very varied with some of the very first participants joining the study potentially still in treatment near three years on though many of those early participants will have terminated treatment so not be "right censored". Of course far more of the recently recruited participants will be still in treatment and their change only known to that point.

The uncertainties arising from this censoring of outcomes is considered in, and visible in, the findings of survival analyses. We will analyse time to completion of therapy by category of termination and also analyse how baseline predictor variables impact on the slope of those curves. Different survival analytic methods make different assumptions about the relationships between predictors and the time curves, notably whether there is "parallelism" of curves across groups, or not, and these issues will be explored, and the appropriate analyses reported.

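### The missing-data checks the SAP names cannot show how robust mean change, d2 and dz are to the non-MAR missingness it expects

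*SAP*

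**What the plan says.** SAP, Secondary objectives, 5 deals with missing data for the whole plan. It names a challenge "affecting all the above analyses, is that of non-participation", and ranks data loss of other kinds well above omitted items. Its methods paragraph begins "Given that none of the missingness is likely to be truly" MAR, let alone MCAR. It argues that imputation such as MICE "may have limited or no advantages over crude substitutions (means across all participants for the missing data, or means for that participant"), or over listwise or casewise deletion, and concedes that strong bias can result. The commitment is "We will use methods, in the light of the observed patterns of missingness, and report their impacts on analyses as robustness checks", and not as solutions. Refusals, withdrawals and data loss will be described, with attention to time and centre.

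The results affected are in section 3, Primary objective. For (a), baseline/termination change: "We will report both mean change and also effect sizes reporting" d2 and dz, with bootstrap CIs. Analysis (b), the multilevel models, differs in that "all data across all durations of data collection are used rather than just the first and last values". Analysis (c), survival, is there because "at termination of intensive data collection some participants will be still in treatment so their" outcome is known only up to that date. In tranche 3 (section 2, Planned and emergent analyses), participants are "followed-up, where in continued clinical contact with the services, to November 2025".

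No section mentions a delta adjustment, tipping point, pattern-mixture, selection or shared-parameter model, or best/worst-case bounds.

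**The concern.** A robustness check should vary the assumption that is in doubt. Here the doubtful assumption is MAR, and the SAP itself says so. Each named method instead fixes one assumption about the unseen scores:

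- Deletion: mean change is the same in the missing as in the observed.
- Grand mean: every missing score equals the observed mean.
- Participant mean: no change, when only baseline was observed.
- MICE: the missing follow the MAR prediction.

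Inspecting observed patterns does not help to choose among them, because observed data alone cannot distinguish MAR from MNAR.

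The direction is open too. Tranche 3 follow-up exists only for people still in contact, so absence may follow recovery or dropout. A reader given all four results could not tell how different the unseen outcomes would have to be before the reported mean change altered materially.

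**Working it through.** **Inputs.** The SAP gives no n, missing fraction, SD or correlation, so there is no figure to reproduce. Assumed throughout unless stated: scores with SD 1, negative change = improvement, n = 300, fraction missing m = 0.4, baseline–termination correlation r = 0.6, mean change −0.50 under MAR.

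**1. Constant shift.** Let unseen termination scores differ from the MAR prediction by d. Truth = −0.50 + 0.4d. Deletion, grand mean and MI all target −0.50. Participant mean, with only baseline observed, sets change to 0 for the missing: 0.6 × (−0.50) = −0.30.

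| d (SD) | Truth | Deletion, grand mean, MI | Participant mean |
|---|---|---|---|
| −0.5 | −0.70 | −0.50 | −0.30 |
| 0 | −0.50 | −0.50 | −0.30 |
| 0.5 | −0.30 | −0.50 | −0.30 |
| 1.0 | −0.10 | −0.50 | −0.30 |

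The range of the named methods contains the truth only for d from 0 to 0.5. Participant mean is right at 0.5 only because shift and change cancel. In simulation (1,500 runs per cell), MI with the matching shift covered the truth 95–96% of the time.

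**2. Missingness rising with the unseen termination score.** Probit slope 0.7, m = 0.4, truth −0.50. The observed mean termination score is displaced by (0.7/√1.49) × φ(0.253)/0.6 = 0.573 × 0.644 = 0.369 SD towards improvement. So deletion gives −0.50 − (1−r) × 0.369, grand mean −0.50 − 0.369, and participant mean 0.6 × the deletion value. MI is from simulation.

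| r | Participant mean | Deletion | MI | Grand mean |
|---|---|---|---|---|
| 0.7 | −0.37 | −0.61 | −0.71 | −0.87 |
| 0.5 | −0.41 | −0.68 | −0.79 | −0.87 |

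The spread brackets the truth without locating it. Agreement is no safer. In a separate run (30% missing, r = 0.5, logistic slope 0.5), deletion, MAR imputation and grand mean gave −0.58, −0.61 and −0.64: within 0.06 of each other, and all overstating improvement by 0.08 to 0.14.

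**3. Grand mean, even under MCAR.** The variance computed from the filled-in data is [(1−m)·2(1−r) + m]/n. The true variance of the estimate is [1/(1−m) + 1 − 2r]/n. Their ratio is exactly 1−m, whatever r and n. Coverage of a nominal 95% CI is therefore 2Φ(1.96√(1−m)) − 1:

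- m = 0.4: 2Φ(1.518) − 1 = 87%.
- m = 0.2: 2Φ(1.753) − 1 = 92%.

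The dz is multiplied by √{2(1−r)/[(1−m)·2(1−r) + m]}. At m = 0.4 this is √(1.4/1.24) = 1.06 for r = 0.3 and √(0.4/0.64) = 0.79 for r = 0.8.

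**4. What a delta-adjusted analysis would add.** The shift at which the CI for mean change first includes zero solves |change| − m·d = 1.96√(V + m(1−m)d²/n), with V = (1−r²)/(n(1−m)) + (1−r)²/n = 0.64/180 + 0.16/300 = 0.00409. Check for change 0.50 at d = 0.91: left 0.50 − 0.364 = 0.136; right 1.96√(0.00409 + 0.00066) = 0.135.

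| Mean change (SD) | n = 300, 40% missing | n = 150 to 600, 40% missing | n = 300, 20% missing |
|---|---|---|---|
| 0.50 | 0.91 | 0.78–1.01 | 1.81 |
| 0.30 | 0.43 | 0.30–0.52 | 0.91 |
| 0.20 | 0.19 | 0.06–0.28 | 0.44 |

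These shifts differ widely, and none of that information can be had from the four named methods.

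**5. Who is missing in (a).** In contrasting (b) with (a), the SAP implies that (a) uses first and last values. If termination means the last available value, a participant with interim scores is not missing in (a), and m is smaller than under a strict termination score. The SAP does not settle this. Neither reading is itself a check against MNAR.

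**The case against.** The strongest reply is that the SAP is candid. It calls the study exploratory and descriptive, admits that these methods can be strongly biased, offers them as checks only, and describes losses by time and centre. Analysis (b) uses all scores, and (c) handles censoring and analyses time to termination by category. The word methods is also open: MICE is introduced as an example, so other techniques are not excluded. All of this stands and limits the weight of the point. But admitting bias does not measure it, a likelihood-based multilevel model still relies on MAR, and the document names no method that departs from MAR by a stated amount.

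Returning one result whatever the unseen scores were is also not peculiar to the named methods. It holds for anything that uses observed data alone, including unshifted MI and the multilevel model. The remedy is thus an added shift, not a different default.

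Three stronger readings are tempting and not supported:

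- *That the absent default method or selection rule is itself an error.* It is missing detail in a document that calls itself a shortened freeze of a longer one, and analyses outside the plan will be labelled emergent.
- *That the remark on MICE is wrong, or that MI should displace participant-mean substitution.* In both MNAR cells of step 2, participant mean lies closer to the truth than MI (errors 0.13 against 0.21 at r = 0.7; 0.09 against 0.29 at r = 0.5). That closeness comes from errors cancelling, but it gives no ground for preferring unshifted MI.
- *That the primary results are biased by a known amount or in a known direction.* Nothing in the SAP fixes either.

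**Conclusion.** The point holds in a limited form. Given the SAP's own expectation of non-MAR missingness, the checks it names cannot show how sensitive mean change, d2 and dz in (a) are to that mechanism. This follows from the methods themselves and needs no assumed n or missing rate. The sizes do rest on assumptions (bivariate normal scores, 20 to 40% missing, r from 0.3 to 0.8). Within them, the unseen scores can move the true mean change well outside the range of the named methods, and the shift needed to bring the CI to zero runs from 0.06 to 1.81 SD. Grand-mean substitution is a poor option even under MCAR. This is a cheap improvement that should be made; it does not invalidate the plan, and it does not fault (b) or (c).

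**What to change.** Before tranche 2 is analysed, amend the SAP as follows:

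1. **Define termination in (a)**: a score at termination, or the last available value.
2. **Add one delta-adjusted (pattern-mixture) sensitivity analysis to (a)** for participants who ended treatment without that value. Fix the range of shifts in advance, from worse to better than the MAR prediction. Shift BMI in both directions, by diagnosis.
3. **Report mean change, d2 and dz with CIs across the range.** The shift at which the CI for mean change first includes zero may be given as a description, and not as a threshold for effectiveness in an uncontrolled cohort.
4. **In tranche 3, apply the same shifts** to follow-up scores of participants no longer in clinical contact.
5. **State the limits.** Participants still in treatment are not imputed and stay in (b) and (c). Initial refusals have no scores and can only be described.
6. **Do not use grand-mean substitution for missing scores.** If participant-mean substitution is kept, label it as the single assumption of no change when only baseline is observed.

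The cost is SAP wording and some programming, with no new data. The drawback is that the plausible range of shifts is a judgement, which is why it must be fixed beforehand.
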